9.2.2 Hb in the Primary Efficacy Period

Hb for the PEP will be calculated as the average of all Hb measurements from the central laboratory within the three visit windows during Weeks 20 through 26, regardless of intercurrent events. At least 1 Hb measurement is required for the calculation; otherwise, the value will be missing and therefore imputed. The PEP is also called analysis time period 3 (see [Table 1](#)).

9.2.3 Change in Hb from Baseline to the Primary Efficacy Period

The change from baseline will be calculated for each subject as the PEP value minus the baseline value.

9.2.4 Analysis of Change from Baseline in Hb to the Primary Efficacy Period

The primary analysis will use multiple imputation with ANCOVA as the substantive model and will be performed in the randomized population.

All intercurrent events will be handled by treatment policy strategy (see [Section 9.1](#)). Unobserved data after intercurrent events, including hemoglobin outcomes and any covariates to be used in the models, will be imputed with randomized subjects using multiple imputation under fully conditional specification (FSC) method. Under the assumption of FSC, data for each variable with missing values will be imputed with a separate regression model allowing for all available data to be used in the imputation process. For continuous variables, the regression method will be used for imputations. For categorical variables, logistic regression models will be used for binary outcomes, and nominal response logistic regression for nominal responses.

An ANCOVA model will be used to compare the mean change from baseline in Hb between 2 treatment groups with the complete dataset from multiple imputation. The ANCOVA model will contain treatment group, baseline Hb level, and the 2 stratification factors (geographic region and mean weekly darbepoetin alfa dose prior to Screening Visit 2) as predictor variables. The stratification factor assignments at randomization will be used in the analysis.

The data will have shown noninferiority of vadadustat if the lower bound of the 95% confidence interval for the difference in estimated change from baseline in the 2 groups (vadadustat minus darbepoetin) exceeds the noninferiority margin of -0.75g/dL. This ensures a 1-sided alpha of 0.025 for the primary analysis. If the lower limit of the 2-sided 95% confidence interval for the difference between the mean in the vadadustat group and the mean in the darbepoetin alfa group is above zero, superiority will have been established and the finding will be interpreted as providing evidence of a greater change from baseline in Hb for vadadustat relative to the control arm.

The procedure of primary analysis follows these steps:

- 1) Missing data will be imputed separately for each treatment group using FSC method with 100 imputed datasets and 40 iterations from PROC MI. The SAS codes of PROC MI with outcome variables and covariates will be as follows.

[REDACTED]

[REDACTED]

[REDACTED]

[REDACTED]

[REDACTED]

[REDACTED]

[REDACTED]

[REDACTED]

9.2.5 Sensitivity Analyses to the Primary Efficacy Results

To assess the robustness of the findings from the primary analysis, the following set of sensitivity analyses will be performed:

- Primary analysis will be repeated using the FAS population.
- Primary analysis will be repeated using the PP population with the actual treatment received.
- Primary analysis will be repeated with imputation of data which may have been affected by a subject's having received any form of rescue (transfusion or ESA). All per-visit Hb values within four weeks of administration rescue therapy (narrow or broad-on-treatment defined in [Section 6.4](#)) will be set as missing prior to imputation.

- A mixed model for repeated measures (MMRM) will be fit to the observed data only and will be performed in the randomized population.

In the MMRM model, the within-subject correlations will use an unstructured covariance structure (TYPE=UN). In the unlikely situation that this model does not converge, the following variance covariance matrix structures will be used in the order of 1) heterogeneous Toeplitz (TYPE=TOEPH), 2) homogeneous Toeplitz (TYPE=TOEP), and 3) compound symmetry (TYPE=CS).

9.3 Secondary Efficacy Endpoints: Definitions and Analyses

The key secondary efficacy endpoint will be formally analyzed once the non-inferiorities have been established in the primary endpoint for vadadustat QD and TIW regimens.

Mean change in Hb value between Baseline and the secondary evaluation period (average Hb from Weeks 46 to 52) will be analyzed using the same methodology as specified for the primary efficacy endpoint. Sensitivity analyses like those of the primary efficacy endpoint will be performed.

9.4 Other Efficacy Endpoints: Strategies for Analysis

Except for specifying the analysis population, other efficacy endpoints analyses will be performed using the randomized and full analysis population, with the assigned treatment as described in [Section 3.1](#). There will be no correction for multiplicity for these endpoints.

9.4.1 Proportion of Subjects Having Average Hb Values within the Target Range during the PEP (Weeks 20 to 26)

All subjects will be defined as either being in their geography-specific target range (see [Section 2.3](#)) in Weeks 20 through 26 (“yes”) or not (“no”), based on the average Hb value during the three visit windows in Weeks 20 through 26. Subjects with no Hb value in the PEP value will be treated as missing. To ensure uniformity across all analyses, the missing binary outcomes will be computed from the imputed complete dataset in primary analysis (see [Section 9.1.4](#)) [Ratitch, 2013].

The proportion of subjects within target range will be calculated, and a 95% confidence interval of the proportion will be performed by treatment group.

A Mantel-Haenszel estimation of risk difference stratified by the baseline strata will be conducted, and the corresponding 2-sided 95% confidence interval for the risk difference will be calculated. Noninferiority will have been established if the lower limit of the confidence interval is above -15% when tested per the testing procedure ([Section 9.5](#)).

If the lower limit of the 2-sided confidence interval for the risk difference is above zero, superiority will have been established and the finding will be interpreted as providing evidence of a higher proportion of subjects being within the target range for vadadustat relative to the control arm when tested per the testing procedure ([Section 9.5](#)).

The associated odds ratio and corresponding 2-sided 95% confidence interval will also be calculated.

The analysis of proportion of subjects within target range follows these steps:

9.4.2 Proportion of Subjects Having Average Hb Values within the Target Range during the SEP (Weeks 46 to 52)

Proportion of subjects having average Hb values within the target range during the SEP (Weeks 46 to 52) will be analyzed using the same methodology as specified for the PEP (see Section 9.4.1).

9.4.3 Proportion of Subjects Receiving IV Iron Therapy from Baseline to Week 52

The proportion of subjects receiving at least one intravenous (IV) iron therapy from Baseline to Week 52 will be calculated, and a Mantel-Haenszel estimation of risk difference stratified by the baseline strata will be performed.

In addition, the following subgroups of baseline iron will be performed:

- Subjects not receiving any iron at baseline, and
- Subjects receiving IV or oral iron at baseline.

9.4.4 Average Weekly Dose of IV Elemental Iron Administered from Baseline to Week 52

Average weekly dose of IV elemental iron administered from Baseline to Week 52 in subjects who have received IV elemental iron will be calculated, and an analysis of variance (ANOVA) model with 2 stratification factors at randomization will be performed. If the distribution is highly skewed because of a long tail to the right, other methods may be considered.

9.4.5 Receipt of ESA Rescue

The proportion of subjects with any ESA rescue medications including narrow or broad-on-treatment therapies with $\geq 50\%$ or $\geq 100\%$ dose increase in darbepoetin alfa defined in [Section 6.4](#) will be calculated. A Mantel-Haenszel estimation of risk difference stratified by the baseline strata for each study period will be performed.

The time to the first ESA rescue (narrow or broad-on-treatment therapies with $\geq 50\%$ or $\geq 100\%$ dose increase in darbepoetin alfa) will be analyzed by Cox regression model for treatment comparison in the randomized population. The estimated hazard ratio and its 95% CI will be performed. Kaplan-Meier curve will be displayed as well.

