## **9.3 Handling of Missing Data for Primary and Secondary Endpoint Analysis**

It is expected that up to 30% of subjects will discontinue the trial. The reasons for discontinuation will be summarized by treatment arm. Missing Hb values will be imputed using multiple imputation.

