6.4 Rescue Therapy

The narrow and broad-on-treatment rescue therapies are defined as follows:

- Narrow: For all treatment arms, narrow rescue therapy is defined as rescue for worsening anemia with ESA medication or RBC transfusion, not starting after permanent study treatment discontinuation. Reason includes "Hb <9.5 g/dL". For

darbepoetin alfa arm, darbepoetin alfa with increases in dose $\geq 50\%$ or $\geq 100\%$ will be considered as ESA rescue medication.

- Broad-on-treatment: For all treatment arms, broad-on-treatment rescue therapy is defined as any exposure to ESA medication (aside from darbepoetin alfa not designated as rescue in the control arm) or RBC transfusion for any reason not starting after permanent study treatment discontinuation. For darbepoetin alfa arm, darbepoetin alfa with increases in dose $\geq 50\%$ or $\geq 100\%$ will be considered as ESA rescue medication.

Reasons for ESA medication and RBC transfusion will be collected in eCRF. If a given therapy starts the same day as permanent discontinuation of study drug, then that therapy will be considered on treatment for rescue definitions.

In vadadustat arms, any use of ESA may be considered rescue. In darbepoetin alfa arm, since the study drug itself is an ESA, the use of another ESA may be considered rescue, and the increase dose in darbepoetin alfa may be planned titration or a rescue. Subjects treated darbepoetin alfa with increases in dose relative to last dose by percentage of $<50\%$, $\geq 50\%$ and $<100\%$, and $\geq 100\%$. Darbepoetin alfa treatment with $\geq 50\%$ or $\geq 100\%$ dose increases from last dose will be considered as rescue therapies. Subjects will be presented by their maximum category of increase within each of the five analysis time periods (see [Section 5.1](#)).

The time to the first ESA medication or RBC transfusion (narrow or broad-on-treatment therapy with $\geq 50\%$ or $\geq 100\%$ dose increase in darbepoetin alfa) will be analyzed by Cox regression model for treatment comparison in the randomized population. The estimated hazard ratio and its 95% CI will be performed. Kaplan-Meier curve will be displayed as well.

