9.4.6 Proportion of Subjects Receiving Red Blood Cell (RBC) Transfusions

The proportion of subjects receiving RBC transfusions (narrow or broad-on-treatment therapy) will be calculated from Baseline to Week 26 and from Baseline to Week 52. A Mantel-Haenszel estimation of risk difference stratified by the baseline strata will be performed.

The time to the first RBC transfusion (narrow or broad-on-treatment therapy) will be analyzed by Cox regression model for treatment comparison in the randomized population. The

[figure not shown]
estimated hazard ratio and its 95% CI will be performed. Kaplan-Meier curve will be displayed as well.

A table with 8 rows and 3 columns, all of which are completely redacted with black bars.

A table with 10 rows and 3 columns, all of which are completely redacted with black bars.

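### Time to first ESA rescue and first transfusion is displayed by Kaplan-Meier, although study-drug discontinuation and death rule out the event as the SAP defines it and no censoring rule is stated

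*SAP*

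**What the plan says.** **Event definition.** SAP 6.4 defines narrow rescue as "rescue for worsening anemia with ESA medication or RBC transfusion, not starting after permanent study treatment discontinuation". The broad-on-treatment definition has the same cut-off: "RBC transfusion for any reason not starting after permanent study treatment discontinuation". One boundary case is settled there: "If a given therapy starts the same day as permanent discontinuation of study drug", the therapy still counts as on treatment. In the control arm, darbepoetin alfa dose increases of at least 50% or 100% also count, and these too can happen only on study drug.

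**Analysis.** Time to first ESA rescue "will be analyzed by Cox regression model for treatment comparison in the randomized population" (SAP 9.4.5), followed by "The estimated hazard ratio and its 95% CI will be performed. Kaplan-Meier curve will be displayed as well". SAP 9.4.6 does the same for transfusion: "The time to the first RBC transfusion (narrow or broad-on-treatment therapy) will be analyzed by Cox regression model". SAP 6.4 adds the composite of either therapy. SAP Section 19 lists ten such time-to-event tables (14.2.4.4.1 to .4, 14.2.4.6.1 to .2, 14.2.4.7.1 to .4). The readable text names no competing-event estimator and no censoring rule.

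**Proportions.** For ESA rescue, "A Mantel-Haenszel estimation of risk difference stratified by the baseline strata for each study period will be performed". For transfusion, proportions are given to Week 26 and to Week 52.

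**Discontinuation.** Protocol 9.3: "It is expected that up to 30% of subjects will discontinue the trial", with no split by arm. Protocol 8.8.2.1 has study drug stopped at transplant. Protocol 7.3.2 returns discontinued subjects to standard care, including ESAs. SAP 2.2 puts end of study at the follow-up visit 4 weeks after early termination, or at a later date if survival status is determined then.

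**The concern.** After a subject permanently stops study drug or dies, the event in SAP 6.4 can no longer happen. An ESA given the next week as standard care does not count. Discontinuation and death are therefore competing events by the SAP's own definition, not gaps in observation.

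Kaplan-Meier with these subjects censored estimates rescue in a setting where nobody discontinues, on the assumption that those who stopped would have been rescued at the same rate as those who stayed. Protocol 7.3 lists lack of efficacy as a reason to leave, which makes that assumption doubtful for some of them. Readers will take the curve as the share of patients needing an ESA or blood on each regimen. Read that way it can be too high, can disagree with the proportions in SAP 9.4.5 and 9.4.6, and can separate two arms that differ only in how many subjects stopped.

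**Working it through.** The documents give no figure for rescue incidence or for the curves, so there is no stated figure to reproduce. The ranges below are assumptions.

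**Inputs**
- Follow-up: 52 weeks (SAP 2.2). Arm size: 100 (SAP 2.6).
- Stopping before a first rescue, *D*: 20% and 30%. Protocol 9.3 expects up to 30% discontinuation of any kind, and some of those subjects will already have been rescued, so 30% is the upper case.
- Cumulative incidence of the event at Week 52, *r*: 5% to 20% (assumed).
- Constant hazards, with rescue and stopping independent.

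**Formulas**
- Total cumulative hazard = −ln(1 − D − r).
- Rescue part = total × r/(D + r).
- One minus Kaplan-Meier, censoring at discontinuation = 1 − exp(−rescue part).
- Censoring 4 weeks later: with weekly hazards λ (rescue) and μ (stopping), the risk set at time t holds a(t) = exp(−(λ+μ)t) plus x(t), the event-free subjects who stopped in the previous 4 weeks. One minus Kaplan-Meier = 1 − exp(−∫λ·a/(a+x) dt), integrated numerically.
- Standard error of a proportion = √(r(1 − r)/100).

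**Example**, r = 10%, D = 30%: total = −ln(0.60) = 0.5108; rescue part = 0.5108 × 0.10/0.40 = 0.1277; 1 − exp(−0.1277) = 12.0%. The excess is 2.0 points against a standard error of 3.0 points, or 0.66 SE.

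| True incidence | Stopping | 1 − KM, censor at discontinuation | Excess (points) | Excess if censored 4 weeks later |
|---|---|---|---|---|
| 5% | 30% | 6.0% | 1.0 | 0.8 |
| 10% | 30% | 12.0% | 2.0 | 1.7 |
| 15% | 30% | 18.1% | 3.1 | 2.6 |
| 20% | 30% | 24.2% | 4.2 | 3.6 |
| 10% | 20% | 11.2% | 1.2 | 1.0 |
| 15% | 20% | 16.9% | 1.9 | 1.6 |
| 20% | 20% | 22.5% | 2.5 | 2.2 |

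In units of one arm's standard error, censoring at discontinuation with 30% stopping, the excess is 0.44 at 5% incidence (0.97/2.18), 0.66 at 10%, 0.86 at 15% and 1.05 at 20%.

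**Dependence on the censoring rule.** One million subjects were simulated with independent rescue and stopping times, each with a 30% probability by Week 52 in the absence of the other. True incidence was 25.5%. One minus Kaplan-Meier was 30.0% when censoring at discontinuation, 29.4% when censoring 4 weeks later, and 25.5% when event-free discontinuers were kept at risk to Week 52. The bias exists under the first two rules and vanishes under the third.

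**Between arms.** With 15% incidence in both arms and 20% versus 30% stopping, the curves end at 16.9% and 18.1%, a gap of 1.2 points where none exists. With 20% versus 40% they end at 16.9% and 19.6%, a gap of 2.7 points; 40% is above the protocol's overall figure and is only illustrative. The standard error of a difference at 15% incidence is √(2 × 0.15 × 0.85/100) = 5.0 points.

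**When rescue rates differ.** An arm with 30% stopping and 5% incidence is overstated by 1.0 point; an arm with 20% stopping and 20% incidence is overstated by 2.5 points. In points, the larger excess is then in the arm with less stopping. Relative to incidence the order is the other way: 0.97/5 = 19% against 2.54/20 = 13%.

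**The case against.** The strongest reply is that the SAP never says discontinuers are censored. If they stay in the risk set to Week 52, Kaplan-Meier reproduces the cumulative incidence exactly. That stands: a reader might infer that a Kaplan-Meier curve must overstate incidence here, and the documents do not support so flat a statement. It does not clear the plan, because the usual censoring points, last dose and end of study, fall at or near discontinuation. Keeping discontinuers at risk would also turn the Cox estimate from a cause-specific into a subdistribution-type hazard ratio. Two programmers following the text could produce different curves and different hazard ratios.

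A reader might also infer that the arm with more discontinuation is always overstated more, or that one particular arm will be. The first holds for equal rescue rates but can fail in percentage points when rates differ, as shown in the working. The documents say nothing to support the second.

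Other parts of the reply also stand:
- These are other efficacy endpoints, without multiplicity correction (SAP 9.4) and absent from the eight steps in SAP 9.5. No formal conclusion depends on them.
- The crude proportions, taken over all randomized subjects, do not have the bias. With discontinuation and death as competing events, little other censoring remains, so Aalen-Johansen values will nearly equal them.
- Some subjects stop because rescue lasted over 30 days or a second cycle was needed (Protocol 7.3.2). They already had the event, so how informative the remaining stopping is cannot be known from the documents. The calculation does not model it.
- The excess is mostly below one standard error.
- Parts of SAP 9.4 and Section 12 are not readable and could not be checked.

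**Conclusion.** The point holds in conditional form. The event definition makes permanent discontinuation and death competing events, the only time-to-event display is Kaplan-Meier, and the rule that decides whether the curve is biased is missing. Under either usual censoring point, one minus Kaplan-Meier overstates the cumulative incidence. At 30% stopping before rescue and 10% to 20% incidence, the excess is about 2 to 4 points when censoring at discontinuation and about 1.7 to 3.6 points when censoring 4 weeks later. For transfusions, if they are as rare as 5% or less, it is 1 point or less. These sizes rest on assumed constant hazards, independent stopping and assumed incidences; only the 30% ceiling comes from the protocol.

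Equal incidence with unequal discontinuation would separate the curves by a point or two within the protocol's ceiling, well inside sampling error. The primary and key secondary conclusions are untouched. This is worth correcting because it is cheap and makes the curves agree with the SAP's own proportions, not because it threatens the trial.

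**What to change.** In SAP 6.4, 9.4.5 and 9.4.6:

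1. Replace the Kaplan-Meier display with Aalen-Johansen cumulative incidence curves by arm. The competing events are permanent study-drug discontinuation without prior rescue (including for transplant) and death. In the transfusion analysis, prior rescue means a prior transfusion.
2. State that the Cox model censors at those events, and label its result a cause-specific hazard ratio.

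The cost is SAP wording and a standard procedure option on the same dataset; no new data are needed and the sample size is unchanged. The downside is that displayed rates will be slightly lower and the curve no longer maps one-to-one to the Cox hazard ratio, which a table footnote can explain.

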9.4.6 Proportion of Subjects Receiving Red Blood Cell (RBC) Transfusions

The proportion of subjects receiving RBC transfusions (narrow or broad-on-treatment therapy) will be calculated from Baseline to Week 26 and from Baseline to Week 52. A Mantel-Haenszel estimation of risk difference stratified by the baseline strata will be performed.

The time to the first RBC transfusion (narrow or broad-on-treatment therapy) will be analyzed by Cox regression model for treatment comparison in the randomized population. The

[figure not shown]
estimated hazard ratio and its 95% CI will be performed. Kaplan-Meier curve will be displayed as well.

A table with 8 rows and 3 columns, all of which are completely redacted with black bars.

A table with 10 rows and 3 columns, all of which are completely redacted with black bars.

9.4.10 Score of Patient Global Impression of Change (PGI-C)

The PGI-C is a scale that evaluates all aspects of a subject's health and assesses if there has been an improvement or decline in clinical status. Subjects will answer the following question:

- How would you compare the impact of your anemia and its treatment on how you feel now to when you were on the previous treatment (or the period before your last visit)?

The question will be rated as “very much worsened”, “much worsened”, “minimally worsened”, “not changed”, “minimally improved”, “much improved”, or “very much improved”. PGI-C scale score will be summarized by visit and by treatment group.

9.5 Study Level Type I Error Control

The study-wise type I error control for multiple testing of efficacy endpoints is controlled at 0.05 level, two-sided by using hierarchical testing procedure. The order of hierarchy is listed below. Upon the demonstration of the non-inferiority of the primary endpoint of vadadustat QD vs. darbepoetin alfa for the change in average Hb between baseline and the PEP, the non-inferiority of the other primary endpoint of vadadustat TIW vs. darbepoetin alfa for the change in average Hb between baseline and the PEP will be examined with pre-specified margin. If it meets the noninferiority margin, the secondary efficacy endpoints in the list will be examined against the pre-specified statistical criteria and so on. In other words, an endpoint will only be tested against pre-specified statistical criteria when the previous endpoint meets statistical criteria. Once an endpoint did not meet the statistical criteria, any endpoints after it will not be formally tested. The hierarchical testing order will be as follows:

1. Noninferiority of vadadustat QD vs. darbepoetin alfa for the change in average Hb between baseline and the PEP (primary efficacy endpoint).
2. Noninferiority of vadadustat TIW vs. darbepoetin alfa for the change in average Hb between baseline and the PEP (primary efficacy endpoint).
3. Noninferiority of vadadustat QD vs. darbepoetin alfa for the change in average Hb between baseline and the SEP (secondary efficacy endpoint).
4. Noninferiority of vadadustat TIW vs. darbepoetin alfa for the change in average Hb between baseline and the SEP (secondary efficacy endpoint).
5. Noninferiority of vadadustat QD vs. darbepoetin alfa for the proportion of subjects having average Hb values within the target range during the PEP (other efficacy endpoint).
6. Noninferiority of vadadustat TIW vs. darbepoetin alfa for the proportion of subjects having average Hb values within the target range during the PEP (other efficacy endpoint).
7. Noninferiority of vadadustat QD vs. darbepoetin alfa for the proportion of subjects having average Hb values within the target range during the SEP (other efficacy endpoint).

8. Noninferiority of vadadustat TIW vs. darbepoetin alfa for the proportion of subjects having average Hb values within the target range during the SEP (other efficacy endpoint).

10 Safety Analyses

All analyses of safety data will use the safety population.

Most of the analysis of safety data will be descriptive without formal statistical testing. In some cases, 95% confidence intervals for the change from baseline as well as for the difference between the study groups will be reported.

